Aim #1: To determine the effects of CBD on cardiac function in 30 children with DS and LGS. This is the primary aim of the study: The effects of CBD on the cardiac function of 30 children with DS or LGS will be assessed using a 12-lead electrocardiogram (EKG), an optional signal average EKG, and a 24-hour Holter monitor. We hypothesize that there will be no alterations in ventricular repolarization and heart rate variability on the EKGs and Holter monitoring, respectively, after taking CBD for 4-8 weeks, compared to when participants were not taking CBD. *Milestone: Records from 12-lead EKG and 24-hour Holter monitor in 30 patients.*

Note: The following aims are secondary to the primary outcome and goal of assessing the effects of CBD on cardiac function.

Aim #2: To assess signs and symptoms of dysautonomia in the presence and absence of CBD. Signs and symptoms of dysautonomia include parental perception of body temperature, skin color in hands and feet, sweating, pupil size, flushing, feeding issues, heart rate, and constipation. These signs and symptoms will be collected using a previously-established dysautonomia survey. We hypothesize there will be no change in qualitative assessments of signs and symptoms of dysautonomia after taking CBD for 4-8 weeks, compared to when participants were not taking CBD. *Milestone: Completed dysautonomia surveys in 30 patients before and after CBD administration.*

Aim #3: To determine the effects of CBD on the occurrence of seizures. The number of seizures in children who obtain CBD will be assessed using a 7-day seizure diary (Seizure tracker). Caregivers will record the number of

seizures for a 7-day period prior to CBD administration, and repeat the seizure tracking after having received CBD for 4-8 weeks. Change in seizure numbers will be compared pre- and post-CBD administration. We hypothesize that study participants will have lower seizure counts after being on CBD compared to when weren't taking CBD. *Milestone: Completed 7-day seizure diaries in 30 patients before and after CBD administration.*

Study Design and Methodology

[figure not shown]

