Study Design: Thirty patients with DS or LGS who are going to register to take medical cannabis (cannabidiol, or CBD) in the state of Minnesota will be offered the opportunity to participate in this study. If consent is obtained, the patient or guardian will be asked to complete a questionnaire developed for this study that documents observable signs and symptoms of dysautonomia, and to complete a seizure diary for 7 days prior to initially receiving the CBD. Each participant will also have a 12-lead electrocardiogram (EKG), an optional signal average EKG, and wear a 24-hour Holter monitor, all non-invasive measures of cardiac function, prior to being administered the CBD. The EKGs and 24-hour Holter monitor will be interpreted by a cardiac electrophysiologist and will be reviewed for heart rate variability parameters. The dysautonomia questionnaire, seizure diary and cardiac measurements will be repeated 4-8 weeks after the subject has been on a stable regimen of CBD. This time-frame is based on availability of subjects schedules and clinic visits, and it is also greater than 5 half-lives previously reported for CBD (apparent half-life, 21 hours, (15)). Steady-state levels are achieved after 5 half-lives of drug dosing, thus we expect to be at steady-state concentrations.

Subjects who are already on a stable regimen of CBD, yet plan to stop taking CBD at some point for some reason, are also eligible to participate. The patient or guardian will complete the dysautonomia questionnaire and seizure diary (and research staff will be available to help with questions), and the patient will have the 12-lead EKG, an optional signal average EKG, and 24-hour Holter monitor while still on the CBD. The subjects will then come back 4-8 weeks after their last dose of CBD to have these assessments repeated while off of the CBD. Again, this time frame is based on availability of subjects schedules and clinic visits as well as being substantially greater than 5 half-lives of CBD, the standard wash-out period for pharmacological studies.

Sample Size: A power analysis was not used to determine sample size. Current sample size expectations will be 40 subjects based on the number of patients who enroll in the Minnesota state registry and who are also patients at Gillette. This available sample size will allow us to account for potential participant dropout or incomplete data so that we can achieve our target of 30

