patients. This is a pilot study with a limited number of participants, and data collected will be used in a subsequent power analysis to determine the number of subjects needed in a larger study to determine statistical significance. This will be the first study of medical cannabis' effects on autonomic function in children with severe seizures, and due to the anticipated small sample size, these findings will primarily be used as pilot data to guide further characterization of CBD effects on autonomic parameters.

Methodologies: The 12-lead EKG will be used to collect information on rhythm, a detailed assessment of heart rate (RR interval), PR interval, QRS duration, QT and QTc interval, and ST segment changes in order to detect cardiac arrhythmias and other abnormalities (see graphic below). The signal average EKG will take this same information and average them during a 20 minute time period, provided our subject is able to lie still for that amount of time.

Heart rate variability (HRV) will be assessed using the 24-hour Holter ECG recordings. Both time-domain parameters (RR interval [heart rate], SDNN [standard deviation of RR intervals] and SDNN-I [the mean of standard deviation of all RR intervals for all 5 minute segments]) and frequency-domain parameters (VLF [total spectral power of all NN intervals between 0.003 and 0.04Hz], HF [total spectral power of all NN intervals between 0.15 and 0.4Hz] and LF [total spectral power of all NN intervals between 0.04 and 0.15 Hz] amplitude) will be obtained. HRV is a measure of sympathetic/parasympathetic cardiac autonomic balance, with lower HRV parameters indicating increased adrenergic tone.

Data Analysis: The number of participants (30 subjects) is small due to the limited number of patients available for enrollment into this specialized study. The study is an observational study with a cross-over design, where the patients will serve as their own controls. Primary assessments will include determination of any changes in EKG parameters and Holter heart rate variability parameters

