pre- and post-treatment with CBD, as well as the percentage of items in the dysautonomia survey that changed and the number of seizures that occurred pre- and post-treatment with CBD. Appropriate data assessments will be performed to determine whether parametric or nonparametric analyses are the proper approach. Due to the small sample size and potentially highly variable or skewed data due to the complex patient population under investigation, we plan to normalize Holter heart rate variability parameters and EKG parameters and calculate change from “baseline” (off – CBD) to those collected while CBD is being administered at steady-state levels.

We also will compare reported seizure data collected from subjects who enrolled in the study prior to initiation of CBD to those who were already on CBD and then discontinued CBD use to determine if substantial differences are apparent in the two groups, since parent report may be biased. We will also confirm that EKG and Holter monitor data 4-8 weeks post-CBD (from patients who were on CBD but subsequently discontinued use) are not significantly different from baseline data acquired from patients with no previous CBD use, prior to combining all “off – CBD” as baseline values.

Study Participation

The Principal Investigator or research team members will identify subjects who have registered or plan to register with the State of Minnesota to take medical cannabis. Each participant will be in the study for approximately 2 months, and will need to visit Gillette twice. If subjects have not been on CBD, they will make one visit one week prior to starting CBD treatment and one visit after having been on CBD for 4-8 weeks. For subjects that are already on a stable regimen of CBD, yet plan to stop taking CBD at some point, their participation will last 4-8 weeks after their last dose.

Risks and Discomforts

EKG: There is no pain during an EKG; however, the EKG patches may be cold and removing the pads may make the skin red and sore. In some cases, the locations where the EKG patches are placed may need to be shaved.

24-hour Holter monitor: There is no pain during the use of a 24-hour Holter monitor; however, the patches may be cold and removing the pads may make the skin red and sore. In some cases, the locations where the patches are placed may need to be shaved.

Subject Protection

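### EKG and Holter changes are pooled across two family-chosen orders with no visit term, so unequal numbers of starters and stoppers leave part of a shared visit change in the CBD effect

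*Combined protocol and SAP*

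**What the plan says.** All references are to the combined protocol and SAP.

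- **Design label** (Study Design and Methodology, Data Analysis): "The study is an observational study with a cross-over design, where the patients will serve as their own controls".
- **Starters** (Study Participation): "they will make one visit one week prior to starting CBD treatment and one visit after having been on CBD for 4-8 weeks". They are measured off CBD, then on.
- **Stoppers** (Study Design): "Subjects who are already on a stable regimen of CBD, yet plan to stop taking CBD at some point for some reason, are also eligible". They are measured on CBD, then off, 4–8 weeks after the last dose.
- **Visits** (Study Participation): "Each participant will be in the study for approximately 2 months, and will need to visit Gillette twice". So each child contributes one order, and that order follows the family's decision. No randomisation is described.
- **Contrast** (Data Analysis): EKG and Holter heart rate variability parameters are normalised, and a change is calculated from the off-CBD baseline "to those collected while CBD is being administered at steady-state levels".
- **Check before pooling** (Data Analysis): the stoppers' off-CBD EKG and Holter data are to be confirmed as values that "are not significantly different from baseline data acquired from patients with no previous CBD use, prior to combining all" off-CBD values as baseline.
- **Seizures**: Aim #3 says "Change in seizure numbers will be compared pre- and post-CBD administration". Data Analysis adds a comparison of reported seizure data between starters and stoppers, because parent report may be biased.

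The plan names no visit, period or order term and arranges no balance between the two groups. It gives neither check a rule for what happens if the groups differ.

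**The concern.** Using each child as its own control removes stable differences between children. It does not remove anything that changes between the first and second visit. A child may be more settled with the clinic and the Holter at the second visit, which could move heart rate and heart rate variability without any CBD effect. In starters such a change adds to the on-minus-off difference. In stoppers it subtracts from it.

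Having both orders therefore gives the study a way to separate a shared visit change from the CBD effect, but a pooled mean does not use it. Whatever does not cancel is read as CBD. The primary aim hypothesises no alteration in repolarisation or heart rate variability, so the leftover could create a false signal or hide a real one. The data are also meant to feed the power analysis for a larger study, so an error here would carry forward.

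**Working it through.** **The plan's own figures.** The target is 30 analysed children out of 40 expected, set by availability. The plan gives no power, effect size or SD, so there is no calculated sample size to reproduce. It also gives no starter/stopper split; every split below is an assumption.

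**Share of a common visit change kept by pooling.** Let τ be the CBD effect, D the visit-2-minus-visit-1 change common to both groups, n1 the number of starters, n2 the number of stoppers, and N = n1 + n2.

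- Starters, on minus off: τ + D
- Stoppers, on minus off: τ − D
- Pooled mean: [n1(τ + D) + n2(τ − D)]/N = τ + D × (n1 − n2)/N

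For example, at 24:6 the share is (24 − 6)/30 = 0.60.

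**Order-adjusted estimate.** The simple average of the two group means is [(τ + D) + (τ − D)]/2 = τ. In units of the SD of change, the pooled standard error is 1/√30 = 0.183 and the adjusted one is 0.5 × √(1/n1 + 1/n2). At 24:6 this is 0.5 × √(0.0417 + 0.1667) = 0.228.

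**False-positive rate of the pooled test.** This was simulated 40,000 times per split with N = 30, no CBD effect, normally distributed changes and a two-sided 5% paired t-test. The plan leaves the choice of test open, so this is an illustration.

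**Power of the off-CBD check.** Two-sample t-test, 28 degrees of freedom, two-sided 5%, with an assumed difference of 0.5 between-child SD. The noncentrality is 0.5/√(1/n1 + 1/n2). At 20:10 it is 0.5/0.387 = 1.29, giving power of 24%.

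| Starters:stoppers | Share of D kept | False positives, D = 0.3 SD | False positives, D = 0.5 SD | Adjusted SE | Power of off-CBD check |
|---|---|---|---|---|---|
| 30:0 | 1.00 | 36% | 75% | not estimable | not possible |
| 27:3 | 0.80 | 24% | 53% | 0.304 | 13% |
| 24:6 | 0.60 | 14% | 30% | 0.228 | 19% |
| 20:10 | 0.33 | 7% | 10% | 0.194 | 24% |
| 15:15 | 0 | 4% | 3% | 0.183 | 26% |
| 10:20 | −0.33 | 7% | 10% | 0.194 | 24% |

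The adjusted estimate had no bias and a 5.0% false-positive rate at every simulated split with stoppers.

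**What the off-CBD check measures.** It sets stoppers at visit 2 against starters at visit 1. The expected difference is D, plus any difference between the two kinds of children, plus any residual CBD effect. A significant result would not say which of these is at work, and a non-significant one leads straight to pooling.

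**If the visit change is not common.** Write D1 for starters and D2 for stoppers, with the same τ in both. The adjusted estimate is then τ + (D1 − D2)/2, so half the difference remains. If the CBD effects also differ, the average weights the two groups equally whatever their size.

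**The case against.** Four things can be said for the plan.

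1. *It is a cross-over in form.* A reader might infer that no child crosses over. The documents do not support that: every child changes state once, and one order per child is also the rule in a standard two-period cross-over. What sets this study apart is that the order is not randomised and no visit or order effect is modelled. The plan already calls itself observational, which is fair, but that word does not deal with the pooling.

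2. *The plan checks before it pools.* True, and a shared visit change would appear in the off-CBD check. The starter/stopper seizure comparison could show one too: if it compares changes, and the CBD effect is the same in both groups, the expected difference is 2D. But the first check has low power, and neither has a stated consequence if the groups differ.

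3. *The wash-out is long.* At the plan's 21-hour half-life, 4 weeks is 4 × 7 × 24/21 = 32 half-lives. That answers carry-over of the drug, not visit effects.

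4. *This is a pilot with no power claim.* This limits how serious the point is. It does not make the pooled estimate a sound input to the next study.

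A reader might also infer a false seizure reduction of a definite size. The sentences on change from baseline and on combining cover EKG and Holter data only, and the plan does not say whether seizure changes are pooled. The same bias would apply if they were, but the documents supply nothing from which to size it.

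**Conclusion.** The point holds for the pooled EKG and Holter analysis. The order is self-selected, no visit or order term is planned, and the pooled on-minus-off mean keeps (starters − stoppers)/N of a visit change common to both groups: a third at 20:10, 60% at 24:6, 80% at 27:3. The formula is exact for a common change; the splits and the size of D are assumptions.

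It would be too strong to say that the whole of every visit change enters the CBD effect. That happens only with no stoppers, and at 15:15 a common change cancels. Nothing in the plan arranges such a balance. It would also be too strong to say that adjustment cures the problem. Adjustment removes only a common visit change and assumes the same CBD effect in both groups. Changes tied to why a family started or stopped, such as a bad spell or a poor response, can differ between groups and would remain even at 15:15.

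For an exploratory pilot this is a worthwhile, inexpensive improvement to the analysis, not a reason to redesign the study.

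**What to change.** 1. In Data Analysis, replace the cross-over label with: a non-randomised, self-controlled before-after study in two self-selected orders.
2. For every EKG, Holter, survey and seizure outcome, report the within-child on-minus-off change with a confidence interval, separately for starters and stoppers. State whether seizure changes will be combined.
3. Do not use the non-significance check as the licence to pool. Show the off-CBD group difference with its interval as description.
4. Beside the pooled mean, report an order-adjusted estimate: the simple average of the two group mean changes, or a model with a visit term. State that it removes only a visit change common to both groups and assumes the same CBD effect in each, so changes linked to the reason for starting or stopping remain.
5. Set in advance a minimum number of stoppers for the adjusted estimate. Below it, report the starters' result as *change after starting CBD*, without attributing it to CBD.

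No new visits, patients or measurements are needed. The cost is precision: in SDs of change, the standard error is 0.18 for the pooled mean against 0.19 (20:10) or 0.23 (24:6) for the adjusted estimate. At 27:3 it would be 0.30, which shows why item 5 is needed.

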Summary of Background
DS and LGS are severe forms of epilepsy that are largely unresponsive to current AEDs
SUDEP is a major cause of mortality with intractable forms of epilepsy such as DS and LGS
Dysautonomia and increased risk for cardiac abnormalities may play a role in causing SUDEP in patients with highly refractory epilepsy
Modulating autonomic nervous system tone may affect seizure control and risk for SUDEP
Cannabidiol may have an effect on the autonomic nervous system and is now being studied as a potential treatment for refractory epilepsy
Cannabidiol is being obtained from state-licensed pharmacies without having undergone study in clinical trials, and thus, has not been well-characterized
This study will determine if Cannabidiol obtained from state-licensed pharmacies has any effects on cardiac rhythm and reduction in seizures

Rationale for Conducting the Study

Although marijuana has been in use for centuries, CBD has not been well studied as an antiepileptic medication for use in children. Little is known about the autonomic effects of CBD in general, and virtually nothing is known about

the effects that CBD might have on the cardiac function of children with DS or other severe forms of epilepsy. Currently, industry sponsors are conducting studies of CBD in connection with clinical trials of their study drugs. However, similar studies of CBD when administered as an artisanal oil derived from other sources have not been reported.

We propose to study the effects of CBD on cardiac electrical function and the autonomic nervous system in children with DS and LGS, when the CBD was administered as an artisanal oil obtained through state dispensaries or other sources. Our intent is to begin to assess potential risks and benefits of this therapy in a vulnerable patient population by characterizing the effects of CBD on EKG findings, heart rate variability and the occurrence of seizures.

Specific Aims/Study Objectives

This is a pilot study to explore the effects of cannabidiol (CBD) on autonomic cardiac function in children with DS or LGS when the CBD was administered as an artisanal oil. This will be achieved by addressing the following specific aims.

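### The stated on/off-CBD EKG comparison, change in normalized parameters, does not serve the EKG's detection purpose: rhythm has no analysis, and a marked QTc change in one or two children would barely register.

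*Combined protocol and SAP*

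**What the plan says.** **Purpose of the EKG.** Methodologies lists rhythm, RR, PR, QRS, QT and QTc, and "ST segment changes in order to detect cardiac arrhythmias and other abnormalities". The Rationale states the wider aim: "Our intent is to begin to assess potential risks and benefits of this therapy in a vulnerable patient population".

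**Hypothesis.** Aim #1, the primary aim: "We hypothesize that there will be no alterations in ventricular repolarization and heart rate variability on the EKGs and Holter monitoring", comparing on-CBD with off-CBD.

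**Analysis.** Data Analysis: "Primary assessments will include determination of any changes in EKG parameters and Holter heart rate variability parameters" before and on CBD. The method is to normalize the EKG and Holter parameters and calculate change from the off-CBD value, with the choice between parametric and nonparametric analysis left to the data. The only other EKG analysis compares off-CBD values between the two entry groups before pooling them.

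**Reading of tracings.** Study Design, and the Data and Safety Monitoring Plan, have a cardiac electrophysiologist interpret all EKGs and Holter recordings. No section defines an abnormal EKG, sets a QTc cutoff, says how rhythm and ST readings are coded, or calls for a count of children whose reading changed.

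**Size.** "The number of participants (30 subjects) is small due to the limited number of patients available for enrollment". Sample Size adds that "A power analysis was not used to determine sample size".

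**The concern.** Detecting an arrhythmia or other abnormality is a question about each child. The analysis stated is a comparison of numeric parameters. The two do not meet in two places.

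First, rhythm is a category. It has no normalized value and no numeric change, so the stated method gives it no off/on comparison. ST can enter only if deviation is recorded as a number, which the plan does not say.

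Second, QTc is numeric, but a group-level change can stay near zero when a few children move a long way and the rest do not move.

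This matters because the primary hypothesis is one of no change. A null group result would naturally be read as support for it. The background section names sudden death as a major cause of mortality in these epilepsies and suggests that cardiac abnormalities may contribute. An effect confined to a few children is therefore the kind of finding the study should be able to report.

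**Working it through.** There is no power calculation or QTc figure in the plan to reproduce. The check asks how visible one or two marked QTc changes would be in a group comparison.

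**Inputs**
- From the plan: n = 30 paired changes.
- Assumed, because the documents give nothing: SD of paired QTc change 10 to 25 ms; true change 0 in unaffected children; +60 ms in k = 1 or 2 affected children; two-sided 5% level.
- The millisecond scale is used because the normalization is not defined.

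**Step 1: shift in the mean.** k × 60 / 30 gives 2.0 ms for one child and 4.0 ms for two.

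**Step 2: why a t-test does not pick this up.** The affected children also inflate the variance, by 60² × k(30 − k) / (30 × 29): 120 for k = 1 and 231.7 for k = 2. With SD 20:
- k = 1: SD = √(400 + 120) = 22.8; SE = 22.8/√30 = 4.16; ratio 2.0/4.16 = 0.48.
- k = 2: SD = √(400 + 231.7) = 25.1; SE = 4.59; ratio 4.0/4.59 = 0.87.

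Both are far below the critical value of 2.045 (29 degrees of freedom).

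**Step 3: simulated rejection rates** (4,000 sets per row for the t-test, 1,500 for the signed-rank test; simulation error under 1 percentage point).

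| SD (ms) | Children at +60 ms | Mean (ms) | Median (ms) | t-test | Signed-rank |
|---|---|---|---|---|---|
| 10 | 1 | 2.0 | 0.4 | 3.4% | 4.7% |
| 10 | 2 | 4.0 | 0.9 | 8.0% | 7.7% |
| 15 | 1 | 2.0 | 0.7 | 4.3% | 4.5% |
| 15 | 2 | 4.0 | 1.3 | 8.4% | 6.7% |
| 20 | 1 | 2.0 | 0.9 | 4.5% | 4.4% |
| 20 | 2 | 4.0 | 1.8 | 8.6% | 6.6% |
| 25 | 1 | 2.0 | 1.0 | 5.4% | 5.3% |
| 25 | 2 | 4.0 | 2.0 | 7.8% | 6.5% |

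With no affected child, rejection is about 5%. One affected child cannot be told from none, and two barely can. A larger shift does not rescue the tests: at +100 ms the t-test rejects in 1 to 5% (one child) and 4 to 9% (two), and the signed-rank test in 4 to 5% and 7 to 8%.

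**Step 4: what child-level counts would give.** Exact two-sided 95% limits:
- 0/30: 0 to 11.6% (upper limit 1 − 0.025^(1/30))
- 1/30 = 3.3%: 0.1 to 17.2%
- 2/30 = 6.7%: 0.8 to 22.1%

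An exact McNemar test with all changes in one direction has p = 2 × 0.5^d, which falls below 0.05 only from d = 6 (p = 0.031). The counts are descriptive and should not be tested.

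**Step 5: dependence on the cutoff.** With SD 20 and no CBD effect, the expected number above an illustrative +30 ms is 30 × P(Z > 1.5) = 30 × 0.0668 = 2.0 children, and the chance of at least one is 1 − (1 − 0.0668)^30 = 87%. Above +60 ms it is 30 × P(Z > 3) = 30 × 0.00135 = 0.04. These values only show the sensitivity; neither is a recommended cutoff.

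**The case against.** A reader might infer that individual results are discarded and that the EKG is analysed only as a group mean. The text does not support this. Data Analysis says what the primary assessments will include, which is not exclusive. It never says mean, and because each child is his or her own control, the planned variable is a per-child change. An electrophysiologist reads every tracing, so a marked abnormality would probably be noticed for that child. These points stand. What remains is narrower: nothing in the plan carries those readings into an off/on comparison or a reported result.

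A reader might also infer that ST findings cannot be analysed at all. That is too strong, since ST deviation can be measured as a number. Only rhythm is clearly outside the stated method.

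The QTc inputs are assumptions, and non-significance is a limited criticism of a declared pilot that leaves significance to a larger study. The 11.6% limit follows from having 30 children, and the added table would not change it. All of this is fair. Pilot status excuses the lack of power, but it does not excuse the lack of a descriptive count when the hypothesis is no change and the stated purpose is detection.

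Finally, a count without a concurrent control can mislead if the cutoff is low, as step 5 shows. This is a real downside and belongs in the report.

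**Conclusion.** The concern holds as a mismatch between the purpose stated for the EKG and the one on/off-CBD EKG analysis stated. Rhythm has no analysis under that method, and ST has one only if it is recorded numerically. For QTc, under the assumed +60 ms in one or two of 30 children and an SD of 10 to 25 ms, a group test rejects in about 3 to 9% of trials, against 5% when nothing has happened. Support for no alteration in ventricular repolarization could therefore be claimed while one or two children had marked changes.

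The documents do not show that such changes would go unseen clinically, or that the investigators intend to report only a group figure. The gap is in what the plan commits to analyse and report. It should be closed because doing so changes what the trial can conclude and uses readings already being made.

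**What to change.** Add to Data Analysis, as a descriptive supplement:

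- A within-child table of the electrophysiologist's reading (normal or abnormal) off CBD against on CBD, separately for rhythm, ST and QTc.
- The number of children with a new abnormality, with a resolved abnormality, and with a QTc value or increase beyond a cutoff, each with exact 95% confidence limits. The investigators choose the cutoff and the definition of abnormal, and record both before off and on readings are compared.
- A statement that this table appears beside any conclusion of no alteration, and that 0/30 is compatible with a true rate of up to 11.6%.
- A caution that the counts are descriptive, have no concurrent control, and depend on the cutoff, because ordinary variation alone will put some children beyond a low one.

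Individual off/on line plots for QTc are optional. The cost is one table and a short paragraph, with no new visits, recordings or patients. The price is a more modest conclusion.

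### The only summary stated for Aim 2, an unsigned percentage of changed survey items, does not separate signs that improved from signs that worsened on CBD

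*Combined protocol and SAP*

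**What the plan says.** Aim #2 (Specific Aims/Study Objectives) is "To assess signs and symptoms of dysautonomia in the presence and absence of CBD". The hypothesis reads "We hypothesize there will be no change in qualitative assessments of signs and symptoms of dysautonomia after taking CBD for 4-8 weeks", and the same sentence goes on to name the time off CBD as the comparator. On content, the aim states: "Signs and symptoms of dysautonomia include parental perception of body temperature, skin color in hands and feet, sweating, pupil size, flushing". Three more areas (constipation, heart rate and feeding) complete the list, which makes eight areas. The milestone is 30 children with surveys on both occasions. The number of items and the response scale are not given.

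The Study Design paragraph enrols two kinds of children. Starters are assessed off CBD first and on CBD second. Stoppers are assessed in the reverse order: "The subjects will then come back 4-8 weeks after their last dose of CBD to have these assessments repeated while off of the CBD".

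The Data Analysis paragraph describes a design "where the patients will serve as their own controls" and lists, among its primary assessments, "the percentage of items in the dysautonomia survey that changed". The note after Aim #1 classes Aim 2 as secondary. No score, sign, per-item rule or threshold for the survey appears anywhere else. For the cardiac measures the same section is more explicit: "we plan to normalize Holter heart rate variability parameters and EKG parameters and calculate change from" the off-CBD state to the on-CBD state. It also plans a comparison of seizure reports by enrolment group, citing possible bias in parent report.

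**The concern.** A percentage of items that changed adds improvements and deteriorations together. If CBD cleared some signs, or caused the same number, the reported figure could be identical. A third case, in which parents simply answer differently at two visits some weeks apart, also gives a non-zero figure, and the plan offers nothing to compare it with.

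The study is meant to begin assessing risks and benefits and to supply pilot data for sizing a later study. An unsigned percentage gives no directional effect estimate for either purpose. If the directional summary is chosen only after the parent-reported data have been seen, the choice is open to selection.

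**Working it through.** The documents give no figure for Aim 2, so there is none to reproduce. The check is a bound on what one value of the stated measure can mean.

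**Inputs.** N = 30 children (Aim #2 milestone). K = 8 items, each present or absent: an assumption that takes the eight listed areas as one item each. Percentage changed = 20%: chosen for illustration.

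**Formulas.** Let B be the item pairs better on CBD than off, and W those worse.
- Percentage changed = (B + W) / (N × K)
- Net change in abnormal signs per child = (W − B) / N

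**Numbers.** N × K = 30 × 8 = 240 item pairs. 20% of 240 = 48 changed pairs.

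| Better | Worse | Percentage changed | Net signs per child |
|---|---|---|---|
| 48 | 0 | 20% | −48/30 = −1.6 |
| 36 | 12 | 20% | −24/30 = −0.8 |
| 24 | 24 | 20% | 0 |
| 12 | 36 | 20% | +24/30 = +0.8 |
| 0 | 48 | 20% | +48/30 = +1.6 |

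The extremes require at least 20% of items to be abnormal off CBD (for −1.6) and at least 20% to be normal off CBD (for +1.6).

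**Dependence on the assumed item count.** The bound is ±0.20 × K signs per child: ±1.6 for K = 8, ±3.0 for K = 15, ±6.0 for K = 30. As a share of items it is always −20% to +20%.

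**Dependence on the unit.** The plan does not say whether the percentage is per child, per item or pooled. The ambiguity is the same at each level. A child with 2 of 8 items changed scores 25%, whether both cleared (net −2), both appeared (net +2) or one did each (net 0).

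**Is the unambiguous value, 0%, likely?** Suppose each answer flips by chance with probability r, independently (an assumption). Then P(0% over all children) = (1 − r)^240. For r = 2% this is 0.98^240 = 0.008, and for r = 10% it is about 1 × 10⁻¹¹. A non-zero result should be expected even without any drug effect.

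**Visit order.** The unsigned percentage is the same whichever visit came first. A signed version is not. If items were scored as second visit against first, an improvement on CBD would count as better in a starter and as worse in a stopper, and the two would cancel when combined.

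**The case against.** The strongest reply is that the hypothesis has no direction. It predicts no change, and the share of items that changed is a direct measure of that. This stands. A reader might infer that the planned summary cannot speak to the hypothesis at all, but the documents do not support that reading: 0% would show no change, and the complement is the share unchanged. The unsigned percentage also has a merit that net change lacks. In the 24/24 row above, net change is zero although 20% of items moved. What is missing is direction, and a benchmark for chance variation.

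A reader might also infer that the plan leaves the survey without an off-CBD reference, because the Data Analysis section spells one out only for EKG and Holter data. That is not supported either. The Aim #2 hypothesis itself names the off-CBD state as comparator. What is absent is its restatement as a scoring rule, which matters only once direction is scored.

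Two further replies have some force. The Data Analysis list is introduced as what the assessments will include, so it need not be exhaustive. Counting both directions alike is the literal reading of the phrase, not a stated scoring rule. Still, no other Aim 2 summary is given. Finally, direction can be derived later from the completed surveys. This is true, and it limits the loss to a pre-specified summary.

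**Conclusion.** The concern holds in a limited form. The one summary stated for Aim 2 does not distinguish improvement from worsening, so any non-zero value fits net benefit, net harm or no net change. With 8 present/absent items and 30 children, 20% changed covers −1.6 to +1.6 signs per child. The item count, the response scale and the 20% are assumptions, but the ambiguity itself needs none of them.

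It is minor. Aim 2 is declared secondary in a pilot without a power analysis, the primary cardiac aim is untouched, and no information is lost.

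**What to change.** Keep the percentage changed and add to the Data Analysis section text along these lines:

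- Each survey item will be classed as better, unchanged or worse on CBD relative to off CBD. Starters and stoppers will be scored in this same off-to-on direction whatever the visit order.
- The percentages better and worse will be reported separately, overall and per item.
- The per-child net change in number of abnormal signs will be given as a paired estimate with a 95% CI.
- Absence of change will be described from these estimates and their intervals, and will not be concluded from a non-significant test.

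A descriptive display by enrolment order, parallel to the one planned for seizure reports, is a reasonable option because the survey is also parent-reported. It is separate from the main change.

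**Cost.** A few sentences and a short scoring key, with no new visits or data. The key must define better and worse for items that can be abnormal in either direction, such as body temperature, pupil size and heart rate. With about 30 children the estimates will be imprecise, so an interval that includes zero should not be read as evidence of no change. Net change can hide opposite shifts, which is why both directions are shown per item.
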